## **3.2 Primary efficacy variable**

The primary efficacy variable is the mean change from baseline in HbA1c at Week 24.

#### **3.3** Secondary efficacy variable

The following secondary efficacy variables will be analysed:

- Percent of patients achieving a therapeutic glycaemic response, defined as a HbA1c <7.0% at Week 24
- Mean change in Fasting plasma glucose (FPG) at 24 weeks
- Mean change in total body weight at 24 weeks

#### **3.4** Exploratory efficacy variable

The following exploratory endpoints will be analysed:

- Mean change from baseline in HbA1c at week 6 and 12
- Proportion of patients achieving therapeutic glycaemic response, defined as HbA1c <7.0%, after 12 weeks
- Percent of patients who require glycaemic rescue or discontinue study treatment for lack of efficacy (12 and 24 weeks)
- Mean change in FPG at 6 and 12 weeks
- Mean change in total body weight at 6 and 12 weeks
- Mean change from baseline in systolic BP (6, 12 and 24 weeks)
- Mean change from baseline in diastolic BP (6, 12 and 24 weeks)
- Mean change from baseline HbA1c after 12 weeks in patients whose baseline HbA1c was >8%
- Mean change from baseline HbA1c after 12 weeks in patients whose baseline HbA1c was ≤8%
- Mean change in HbA1c from baseline in patients with baseline >8% at 24 weeks
- Mean change in HbA1c from baseline in patients with baseline  $\leq 8\%$  at 24 weeks
- Proportion of patients achieving HbA1c <7.0% and a weight loss of 2 kg after 24 weeks
- Mean change from baseline of blood biomarker values at 24 weeks

# 3.5 Safety variables

The following safety data will be collected and analysed: AEs/SAEs, clinical chemistry/hematology parameters and vital sign measurements.

#### 3.5.1 Adverse Events

All AEs and SAEs occurring during the study will be recorded. Details such a start and stop date of AE, action take and outcome will be recorded.

#### 3.5.2 Vital sign

Vital sign measurements in this study will include sitting systolic and diastolic BP and heart rate (HR). Vital signs should be measured from Visit 1 after the patient rests for approximately 5 minutes and with the patient in a sitting position, and again as per the schedule of event defined in protocol.

#### 3.5.3 Laboratory Safety Variables

Safety laboratory variables will be analysed including values regardless of rescue but on treatment. On treatment is defined as first dose to last dose + 4 days for all variables except liver function tests (alanine aminotransferase, aspartate aminotransferase, bilirubin and alkaline phosphatase) which will use first dose to last dose + 30 days.

The following laboratory variables will be summarised:

| Haematology/Haemostasis (whole blood)  | Clinical Chemistry (serum or plasma)   |  |  |
|--|--|--|--|
| B-Red blood cell count
Red Blood Count indices:
_Mean Cell Haemoglobin (MCH)
_Mean Cell Volume (MCV)
_Mean Cell Haemoglobin Concentration (MCHC) | S/P-Creatinine. Glomerular Filtration Rate
be calculated by the Central Laboratory usin
the re-expressed abbreviated (four-variable)
Modification in Diet and Renal Disease
(MDRD) formula and results will be reporte
the sites and the Sponsor.             |  |  |
| _White blood cell Count and Differential
_Platelet count  | (Levey AS, Coresh J, Greene T, et al. Expressing the
Modification of Diet in Renal Disease Study
Equation for Estimating Glomerular Filtration Rate
with Standardized Serum Creatinine Values.
Clinical Chemistry 2007; 53:766-72).
S/P-Bilirubin, total (TB) |  |  |
| B-Haemoglobin (Hb)   | S/P-Alkaline phosphatase (ALP)   |  |  |
| B-Haematocrit  | S/P-Aspartate transaminase (AST)
S/P-Alanine transaminase (ALT)   |  |  |
|  | S/P-Uric acid
S/P-Potassium   |  |  |
|  | S/P-Calcium, total
S/P-Sodium   |  |  |
|  | S/P-Chloride
S/P-Bicarbonate  |  |  |
|  | S/P-Magnesium
S/P-Phosphorus
S/P- Total Protein  |  |  |
|  | S/P Creatinine Kinase (CK). Reflex Testing:
Troponin I will be ordered if CK >400IU/L).   |  |  |

Abbreviations: AST aspartate transaminase, ALP alkaline phosphatase, ALT alanine transaminase, B blood, Hb haemoglobin, P plasma, S serum, TB total bilirubin.

#### Urinalysis

Urinalysis assessments will be performed according to Study Plan (Table 1) of protocol and will include the following: blood, protein, albumin, glucose, urine ketones, creatinine and calculated urinary albumin: creatinine ratio.

In addition to the above assessments, hematuria to be defined basing on dipstick urinalysis results (for algorithm please refer to appendix E of protocol) and summarized separately in yes/no table.

## 4. ANALYSIS METHODS

## 4.1 General principles

Continuous data will be summarized in terms of the number of observations, mean, standard deviation (SD), standard error (SE), upper quartile, median, lower quartile, minimum and maximum unless otherwise stated. In addition, 95% confidence interval for the mean (percent) change from baseline will be calculated for continuous efficacy variables. They will be presented by treatment group and time point where applicable. The minimum and maximum will be reported to the same number of decimal places as the raw data recorded in the database. The mean, median, lower quartile and upper quartile will be reported to one more decimal place than the raw data recorded in the database and the SE will be reported to three more decimal places than the raw data recorded in the database and the SE will be reported to three more decimal places than the raw data recorded in the database and the SE will be reported to three more decimal places than the raw data recorded in the database. In general, the maximum number of decimal places reported shall be four for any summary statistic.

Descriptive summaries of categorical variables will consist of frequencies and percentages for each treatment group and overall, where applicable.

Descriptive summaries of change from baseline in categorical variables will be provided using shift tables. Frequencies and percentages of patients within each treatment group will be generated for levels of cross-classifications of baseline and the on-treatment value of the parameter. The on-treatment value can either be the value at a certain time point, or e.g. for laboratory tests, the minimum/maximum value in the direction of toxicity, which has been observed during the treatment period. Treatment group differences will not be assessed in summaries of shifts.

Note, that subjects from one site with potential serious GCP violations will be excluded from all tables and figures. A selection of key tables and figures will be rerun with the site data included to assess the impact of the exclusion. See section 2.2.

## 4.2 Analysis methods

#### 4.2.1 Patient disposition

A clear accounting of the disposition of all patients who enter the study will be provided, from screening to study completion. Summaries of patient disposition will be presented by treatment and overall (column), while summaries in the EPS (when applicable) will be presented only by overall (column). The following patient disposition summaries will be provided:

• Number and percentage of patients in the EPS, FAS, PP and SAF populations will be presented on their own as well as by country, study centre and overall (row) (Analysis Population: EPS).

- Number and percentage of screen-failure patients (i.e., patients enrolled but not randomized), further classified by reasons for screen failure (Analysis Population: EPS).
- Number and percentage of patients who complete the study and who withdraw from the study, further classified by reasons for withdrawal from the study (as recorded on Disposition (DS) page of Case Report Form [CRF]).(Analysis Population: FAS)

## 4.2.2 Demographics and other baseline characteristics

Demographic and baseline patient characteristics will be listed and summarised for the SAF. If the FAS differs significantly from the SAF, the analysis will be repeated for the FAS. All summaries of continuous characteristics will be based on non-missing observations. For categorical characteristics, percentages will be calculated out of the total number of patients in the data set, overall and by treatment group, where applicable (i.e., each denominator includes the number of patients with missing/unknown values for the characteristic).

#### 4.2.2.1 Demography data

Standard descriptive statistics will be presented for the continuous variables of:

- Age (years).
- Weight (kg).
- Height (cm).
- Body mass index (BMI) (kg/m^2), calculated as: weight/(height)

The total frequency counts and percentages of patients will be presented for the categorical variables of:

- Sex (grouped as male, female)
- Age group (years) (grouped as <65,  $\ge 65$  and  $\ge 75$ )
- Race (grouped as White, Black or African American, Asian, Native Hawaiian or Other Pacific Islander, American Indian or Alaska Native, or Other)
- Ethnic group (grouped as Hispanic/Latino, Non Hispanic/Latino)
- Body mass index (kg/m^2) (grouped as Normal ( <25 kg/m^2), Overweight (≥25 kg/m^2 ≤30 kg/m^2), Obese (>30 kg/m^2))
- Geographic Region (grouped as North American/ Other Regions)

## 4.2.2.2 Other baseline characteristics

Standard descriptive statistics will be presented for the continuous variables of:

- Duration of Type 2 Diabetes (years).
- HbA1c
- FPG
- Post-prandial glucose (PPG)

Statistical Analysis Plan Amendment Study Code D1683C00005 Edition Number 4.0 Date 09th Aug 2017 The total frequency counts and percentages of patients will be presented for the categorical variables of:

- Duration of Type 2 Diabetes (years) (grouped as  $< 3, \ge 3$  and  $\le 10$  yrs, > 10 yrs)
- Diabetes Complications (grouped as Any, Retinopathy, Neuropathy Autonomic, Neuropathy Peripheral, Nephropathy Angiopathy, Other)
- HbA1c (grouped as:  $\leq 8\%$ , > 8)

#### 4.2.2.3 Medical History

Diabetes related medical history and general medical history will be coded using Medical Dictionary for Regulatory Activities (MedDRA). All disease related medical history will be listed and the number and percentage of patients with any disease related medical history will be summarised for the FAS by system organ class (SOC) and preferred term (PT).

All general medical history will be listed and summarised similarly.

#### 4.2.2.4 **Prior Medications**

Previous medications, including any medication (other than study medications) with a start date prior to Day 1 of treatment period, will be summarized.

Missing and partial date handling of start and stop dates of previous medications is described in Section 3.1.6.1 above. The AZ Drug Dictionary v16.1is used to code the non-study medication.

#### 4.2.3 Extent of Exposure and Treatment Compliance

#### 4.2.3.1 Extent of Exposure – Study and Rescue Medications

The extent of exposure to each study medication during the treatment period is defined as: treatment end date – treatment start date +1

The extent of exposure to study medication will be summarized using the SAF for the treatment period and the treatment period prior to rescue, where the number and percent of patients with an extent of exposure within specified day ranges (1-7, 8-30, 31-60, 61-90, 91-120, 121-180, > 180 days) will be presented by treatment group.

The mean, standard deviation (SD), median and range of the number of days of exposure to study medication will also be presented. Summaries will be presented including periods of interruptions (defined by record of 0 tablets of study medications on the CRF).

All rescue medication use during the treatment period will be summarized and listed by treatment group.

A listing of patients by batch number of study medication will also be generated.

#### 4.2.3.2 Extent of Exposure – Concomitant Medications

Concomitant medications include any medication taken from start of the treatment period up to the end of the treatment period.

Concomitant medications will be summarized using the SAF dataset by drug class and (generic) drug name. A summary table by drug class and generic drug name will be generated for each of the following:

- all concomitant medication
- all concomitant diuretic medication
- all concomitant anti-hypertensive medication

To identify each type of diuretic medication and anti-hypertensive medication a list of terms will be selected before database lock and unblinding of the database. Missing and partial date handling of start and stop dates of concomitant medications is described in Section 3.1.6.1 above.

#### 4.2.3.3 Measurement of Treatment Compliance

Percent treatment compliance is calculated during treatment period for study medication (i.e. saxagliptin or matching placebo and dapagliflozin or matching placebo) and overall.

(Number of tablets taken / Planned number of tablets)\*100%

Where the planned number of tablets is calculated as:

(End date – Start date +1) \* prescribed daily number of tablets

The number of tablets taken is calculated as:

total number of tablets dispensed - total number of tablets returned

based on the CRF accountability pages.

Overall compliance is defined as :

(Total number of tablets taken / Total planned number of tablets)\*100; where

the planned number of tablets is calculated as:

(latest end date – earliest start date +1) \* prescribed daily number of tablets

and the number of tablets taken is calculated as:

total number of tablets dispensed - total number of tablets returned.

A patient is considered compliant if percent compliance is  $\ge 80\%$  and  $\le 120\%$ . For each type of medication and overall, the number and percent of patients compliant during the treatment period will be displayed for the SAF.

For metformin, a summary for the SAF, including number and percentage of subjects that ever took metformin therapy at a dose of <1500mg per day during the treatment period, will be provided separately in addition to the compliance summary of the study medications.

## 4.2.4 Efficacy analyses

This section addresses separately the analyses to be conducted on the primary efficacy endpoint, on the secondary and other efficacy endpoints.

Summary statistics will be presented for each primary, secondary and exploratory variable as described in Section 4.1, as well as the statistical analyses as described below.

This study is designed to demonstrate the superiority of the co-administered saxagliptin 5mg and dapagliflozin 5mg vs its components in mean change from baseline to week 24 in HbA1c at the 2-sided alpha = 0.05 level.

## 4.2.4.1 Primary efficacy outcome variable

A longitudinal repeated measures analysis using 'direct likelihood' will be performed. The SAS procedure PROC MIXED will be used. The preferred model will include the fixed categorical effects of treatment, week and treatment-by-week interaction as well as the continuous fixed covariates of baseline measurement and baseline measurement-by-week interaction.

The following model will be used:

 $C_{ijk} = intercept + \beta_1 \left[ M_{baseline,ij} \right] + \tau_i + \alpha_k + (\alpha \tau)_{ik} + (\alpha M_{baseline})_{ijk} + error_{ijk}$ 

where

- Cijk is the change from baseline for patient j in treatment group i at time k,
- $\beta_1$  is the slope coefficient for the baseline measurement,
- Mbaseline,ij is the baseline measurement of patient j in treatment group i,
- $\tau_i$  is the mean effect of treatment group i,
- $\alpha_k$  is the mean effect at time k
- $(\alpha \tau)_{ik}$  is the interaction term between treatment group i and time k.
- $(\alpha M_{baseline})_{ijk}$  is baseline measurement-by-week interaction term for patient j in treatment group i at time k, and
- error  $_{ijk}$  is the error term for patient j in treatment group i at time k.

An unstructured matrix for the within-patient error variance-covariance will be used. The denominator degrees of freedom will be calculated according to the Kenward-Roger method.

Statistical Analysis Plan Amendment Study Code D1683C00005 Edition Number 4.0 Date 09th Aug 2017 In case of non-convergence of the preferred model or memory space issues, the following back-up models are defined:

- The first backup model is the same as the preferred model but the Kenward-Roger method will be replaced by Satterthwaite approximation.
- The second backup model is the same as the preferred model but without the term for baseline measurement-by-week interaction.

The second back-up model will only be provided if the first back-up model does not converge or has memory issues.

The model will provide least-squares mean estimates, SE and 2-sided 95% confidence intervals for mean change at all time points within and between treatments.

#### Sensitivity analysis

A sensitivity analysis will be conducted for the primary efficacy using data up to date of rescue medication or prior to the study medication termination + 8 days and will be completed using the same model as described above.

Additional sensitivity analyses of HbA1c changes from baseline at Week 24 (having used SAS procedures PROC MI and MIANALYZE to impute any missing data and analyze the data after imputation, see Section 3.1.6) will be performed using an ANCOVA model at week 24. If the missing data pattern is non-monotone, then the Markov Chain Monte Carlo methodology (MCMC) is first employed to generate a monotone missing pattern (the number of simulation is 1000 and a simulation seed is 725). When the missing data pattern is monotone, then a linear regression will be used to impute the missing HbA1c, i.e. missing values of HbA1c are predicted in turn, given the observed values of HbA1c (a simulation seed is 229).

The per protocol analysis of the primary endpoint, if it is done, will exclude data after rescue or more than 8 days after treatment discontinuation.

For each sensitivity analysis least squares mean estimates and 2-sided 95% confidence intervals for mean changes from baseline within and (when warranted) differences in mean change from baseline between treatments will be provided.

A value of the delta in the tipping point analysis will be reported if it exists.

#### 4.2.4.2 Secondary efficacy variable

The primary endpoint will be tested for saxagliptin plus dapagliflozin versus saxagliptin and dapagliflozin arms simultaneously at the alpha = 0.05 level (two sided). In order to protect the overall type I error rate, the interpretation of the statistical significance of treatment comparisons for each secondary efficacy endpoint will be done using a stepwise procedure. The secondary endpoints then will be tested sequentially as follows:

- 1- saxagliptin plus dapagliflozin versus saxagliptin on percent of patients achieving a therapeutic glycaemic response, defined as a HbA1< 7.0% at Week 24
- 2- saxagliptin plus dapagliflozin versus dapagliflozin on percent of patients achieving a therapeutic glycaemic response, defined as a HbA1< 7.0% at Week 24
- 3- saxagliptin plus dapagliflozin versus saxagliptin on mean change from baseline in FPG at Week 24
- 4- saxagliptin plus dapagliflozin versus dapagliflozin on mean change from baseline in FPG at Week 24
- 5- saxagliptin plus dapagliflozin versus saxagliptin on mean change from baseline in total body weight at Week 24

Each comparison will be tested at the alpha = 0.05 (two-sided) level.

The analysis of the change from baseline for FPG and total body weight at week 24 will be performed using the same longitudinal repeated measures model as for the primary efficacy endpoint.

The proportion of subjects achieving a therapeutic glycemic response (defined as HbA1c <7.0%) at Week 24 will be summarized by treatment group and compared between treatment groups using the methodology of Zhang, Tsiatis, and Davidian [3], and Tsiatis, Davidian, Zhang, and Lu [4]. 95% confidence intervals for the response rate within each treatment group as well as for the difference in response rates between treatment groups will be calculated with adjustment for baseline HbA1c. As defined in Section 3.1.6 patients who did not have A1c measurement at week 24 will be treated as those who did not achieve a therapeutic glycaemic response.

#### 4.2.4.3 Exploratory efficacy variables

The following exploratory endpoints will be analysed using a repeated measure mixed model as was used for the primary efficacy variable:

- The mean change from baseline in HbA1c at week 6 and week 12
- Mean change in FPG at 6 and 12 weeks
- Mean change in total body weight at 6 and 12 weeks
- Mean change from baseline in systolic BP (6, 12 and 24 weeks)
- Mean change from baseline in diastolic BP (6, 12 and 24 weeks)
- Mean change from baseline HbA1c after 12 weeks in patients whose baseline HbA1c was >8%
- Mean change from baseline HbA1c after 12 weeks in patients whose baseline HbA1c was ≤8%
- Mean change in HbA1c from baseline in patients with baseline >8% at 24 weeks
- Mean change in HbA1c from baseline in patients with baseline  $\leq 8\%$  at 24 weeks
- Mean change from baseline of blood biomarker values at 24 weeks

Whilst the following exploratory efficacy endpoints will be summarized by treatment group and compared between treatment groups using the methodology described for analysis of proportion of patients achieving a therapeutic response at week 24, above. 95% confidence intervals for the response rate within each treatment group as well as for the difference in response rates between treatment groups will be calculated with adjustment for baseline HbA1c.

- Proportion of patients achieving therapeutic glycaemic response, defined as HbA1c <7.0%, after 12 weeks
- Percent of patients who require glycaemic rescue or discontinue study treatment for lack of efficacy (12 and 24 weeks)
  - $\circ$  if > 10% require glycaemic rescue or discontinue study treatment for lack of efficacy (12 and 24 weeks) a KM curve will present time to this event.
- Proportion of patients achieving HbA1c <7.0% and a weight loss of 2 kg after 24 weeks

#### 4.2.5 Safety analyses

#### 4.2.5.1 Adverse Events

Adverse Events (AEs) will be classified by Primary SOC and PT according to the MedDRA.

In summaries by SOC and PT, AEs will be sorted by overall decreasing frequency within each SOC and PT. In summaries by PT, AEs will be sorted by decreasing frequency within PT according to the highest of either of the combinational dose group across the study.

Separate pages to capture events of hypoglycemia are contained within the CRF. Hypoglycemia or discontinuation due to hypoglycemia would not be reported on an AE CRF page unless the event fulfilled criteria for an SAE in which case an SAE form would be completed. Hypoglycemia events that are reported as SAEs will be included in all summaries of AEs or SAEs. Separate summaries will be provided including hypoglycemia events reported on the special CRF pages.

#### **All Adverse Events**

An overall summary of adverse events at patient level, including patients who experienced at least one: AE, hypoglycaemic event, treatment-related AE, death, SAE, treatment-related SAE, SAE leading to the discontinuation of study medication, hypoglycaemic event leading to the discontinuation of study medication, and AESI. All AEs (serious and non-serious, excluding hypoglycemic events that are not reported as SAEs) will be summarized by SOC and PT. In addition, a patient listing of all reported AEs will be produced, displaying all events that occurred prior to the start date of treatment period, if any. All AEs (serious and non-serious) including all hypoglycemic events will also be summarized by treatment group, where applicable.

Adverse events and SAEs with an onset from Day 1 of treatment up to and including 4 days and 30 days respectively, after the last dose date in the treatment period will be considered as occurring during the treatment period.

In addition, the following summaries will be provided for the treatment period (excluding hypoglycemic events that are not reported as SAEs):

- Most common adverse events by preferred term and treatment group (i.e., reported by  $\geq 2$  % of patients in any treatment group),
- Adverse events by system organ class, preferred term, intensity and treatment group,
- Adverse events related to study medication by system organ class, preferred term and treatment group.
- Proportion of patients with adverse events by SOC and PT in subgroups of patients defined by age category (< 65 and ≥ 65 years), gender and race.

No formal comparisons will be made between treatments. No formal statistical testing will be performed, only summary statistics will be provided.

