#### 3.9.2 Study-specific discontinuation criteria:

- 1. Initial and repeat laboratory tests meet any of the following criteria (see Appendix D):
  - ALT and/or AST are >3x ULN and TB >2x ULN
  - ALT and/or AST are >5x ULN for ≥14 consecutive days, at any time after initial confirmatory results
  - ALT and/or AST are >8x ULN
- 2. Pregnancy confirmed by a positive pregnancy test or otherwise verified
- 3. Hypoglycaemia episodes as defined in Section 3.9.3

- 4. Use of (need for) any anti-hyperglycaemic medication other than IP or background metformin or rescue therapy allowed by protocol. Insulin use is permitted in the following situations:
  - For up to 14 days in total during the study and up to 7 continuous days if patients are unable to take oral medications (for example during a gastrointestinal illness)
  - For up to 14 days in total during the study and up to 7 continuous days if there
    is a documented illness or infection that requires additional therapy for
    maintaining glycaemic control
  - For up to 14 days in total during the study and up to 7 continuous days if
    patients have to temporarily stop IP and/or metformin due to recommendations
    made in this clinical study protocol
  - For up to 7 days during hospitalisation. When the reason for hospitalisation is the management of the patient's glycaemic control, treatment with insulin is considered a rescue and is allowed for as long as clinically necessary.
- 5. eGFR <60mL/min/1.73m^2 (by MDRD) confirmed by a repeated central lab measurement within 1 week.

**Note**: Withhold the study medication until results for the retest of eGFR are available ONLY for randomisation visit (For all other visits, there is no need to interrupt the study medication)

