#### 6.3.3 Variables

The following variables will be collect for each AE;

- 1. AE (verbatim)
- 2. The date when the AE started and stopped
- 3. Maximum intensity
- 4. Whether the AE is serious or not
- 5. Investigator causality rating against the IP (yes or no)
- 6. Action taken with regard to IP
- 7. AE caused patient's withdrawal from study (yes or no)
- 8. Outcome

In addition, the following variables will be collected for SAEs:

- 1. Date AE met criteria for SAE
- 2. Date Investigator became aware of SAE
- 3. AE is serious due to
- 4. Date of hospitalisation

- 5. Date of discharge
- 6. Probable cause of death
- 7. Date of death
- 8. Autopsy performed
- 9. Causality assessment in relation to Study procedure(s)
- 10. Description of AE
- 11. Whether treatment of AE was required

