#### 6.3.6 Adverse events based on examinations and tests

The results from protocol mandated laboratory tests and vital signs will be summarised in the Clinical Study Report (CSR). Deterioration as compared to baseline in protocol-mandated laboratory values and vital signs should therefore only be reported as AEs if they fulfill any of the SAE criteria or are the reason for discontinuation of treatment with the IP.

If deterioration in a laboratory values or vital sign is associated with clinical signs and symptoms, the sign or symptom will be reported as an AE and the associated laboratory result/vital sign will be considered as additional information. Wherever possible the reporting Investigator uses the clinical, rather than the laboratory term (e.g., anaemia versus low haemoglobin value). In the absence of clinical signs or symptoms, clinically relevant deteriorations in non-mandated parameters should be reported as an AE.

Hyperglycaemia due to insufficient clinical response is not necessarily considered an AE/SAE, unless the Investigator does not consider it expected for that patient, based on an increased frequency or severity in relation to the patient's usual clinical course.

Any new or aggravated clinically relevant abnormal medical finding at a physical examination as compared with the baseline assessment will be reported as an AE.

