### 8.5.6 Exploratory analysis (if applicable)

Analyses for exploratory efficacy endpoints will use the same methodology for binary and continuous endpoints as described above.

Safety analyses will be performed using the Safety analysis set, including data after rescue. The number and percent of patients with at least one adverse event will be summarized for each treatment group, including summaries of AEs, SAEs, AEs leading to discontinuation, and AEs of special interest. Summaries will include the number of patients with events by specified system organ classes and preferred terms. The summary of AEs will be performed both overall and by subgroup. Additionally, the incidence of adverse events and frequency of recurring adverse events will be summarized for each treatment group for both frequent events (occurring in at least 5% of patients) and for selected adverse events of special interest.

Values and changes from baseline at each scheduled time point for clinical laboratory parameters and vital signs, including blood pressure and heart rate, will be summarized by treatment group using descriptive statistics. The number and percent of patients with laboratory values meeting marked abnormality criteria will be summarized for each treatment group and by shift tables. Other safety assessments including serum creatinine, and eGFR by MDRD will be summarized by treatment group using descriptive statistics of values and changes from baseline at each scheduled time point.

Additional analyses for adverse events and laboratory marked abnormalities will be performed excluding data after rescue in the double-blind treatment period. The primary analysis of events of hypoglycaemia will be performed excluding data after rescue, and more than 4 days after study treatment discontinuation.

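### The SAP does not specify two safety outputs promised in protocol section 8.5.6: a summary of all AEs leading to discontinuation, and an AE analysis excluding data after rescue

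*SAP*

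**What the plan says.** Protocol section 8.5.6 makes three commitments on safety:

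- The main analysis keeps post-rescue data: "Safety analyses will be performed using the Safety analysis set, including data after rescue".
- AEs are summarised for each treatment group, "including summaries of AEs, SAEs, AEs leading to discontinuation, and AEs of special interest".
- There is a second run without post-rescue data: "Additional analyses for adverse events and laboratory marked abnormalities will be performed excluding data after rescue in the double-blind treatment period".

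SAP section 4.2.5.1 (All Adverse Events) gives an overview table whose entries on stopping drug are "SAE leading to the discontinuation of study medication, hypoglycaemic event leading to the discontinuation of study medication, and AESI". It then lists four further tables: common AEs, AEs by intensity, AEs related to study medication, and AEs by subgroup. None concerns discontinuation and none excludes post-rescue data.

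SAP section 4.2.5.3 repeats the excluding-rescue commitment for laboratory marked abnormalities only. The Hypoglycemic Events part of section 4.2.5.1 ends its window at rescue, but for those events alone. SAP section 6, which lists changes from the protocol, mentions neither omission.

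**The concern.** The safety objective is to evaluate the tolerability of the combination against each single agent. AEs that make patients stop drug are a main measure of that. The SAP counts them by arm only when they are serious or hypoglycaemic. A non-serious AE of any other kind that stopped drug appears among all AEs, but no table shows that it led to discontinuation.

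The rescue analysis matters because of what rescue is. First-line rescue in every arm is open-label dapagliflozin plus saxagliptin (protocol synopsis and section 4.4), and rescued patients stop blinded drug but stay on their visit schedule. After rescue, a patient randomised to one agent can be taking both. An AE table that includes this time answers one question and a table without it answers another. The protocol asked for both, and the SAP specifies only the first for AEs and SAEs.

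**Working it through.** The plan states no figure on this point, so there is nothing to reproduce. The check is a comparison of text, followed by arithmetic on assumed rates.

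**Step 1. Does another SAP output fill the discontinuation gap?**

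- Patient disposition (SAP 4.2.1) counts patients "who withdraw from the study, further classified by reasons for withdrawal from the study". Under protocol section 3.9.4, patients who stop drug are expected to remain in the study, so this table does not count them.
- The exploratory endpoint on rescue or discontinuation (SAP 4.2.4.3) covers lack of efficacy only.
- AESI summaries follow the pattern of the AE and SAE tables, so they add no discontinuation table.
- The patient listing of AEs is not a summary by arm.

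None fills it.

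**Step 2. Does another SAP output fill the excluding-rescue gap?** Exposure is summarised for the period before rescue (SAP 4.2.3.1), hypoglycaemia is cut at rescue, and marked laboratory abnormalities have their own run. None of these is an AE or SAE summary.

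**Step 3. Size of the first gap.** Inputs: 300 patients per arm (protocol 8.2). Assumed: 1% to 5% stop drug for an AE, and 50% to 90% of these AEs are non-serious and non-hypoglycaemic.

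- Low: 300 × 0.01 × 0.50 = 1.5 patients.
- High: 300 × 0.05 × 0.90 = 13.5 patients.
- Each patient is 1/300 = 0.33 percentage points of the arm.

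**Step 4. Size of the second gap.** Inputs: 300 × 24 = 7,200 patient-weeks per arm with full follow-up; windows of last dose + 4 days for AEs and + 30 days for SAEs (SAP 4.2.5.1). Assumed: 3% to 10% rescued (9 to 30 patients), all at about Week 13, shortly after the Week 12 visit. The SAP does not say which drug last dose refers to, so both readings are shown.

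| Reading of last dose | Events | Post-rescue patient-weeks in the table | Share of 7,200 |
|---|---|---|---|
| Blinded drug | Non-serious AEs | 9 × 4/7 = 5.1 to 30 × 4/7 = 17.1 | 0.07% to 0.24% |
| Blinded drug | SAEs | 9 × 30/7 = 38.6 to 30 × 30/7 = 128.6 | 0.54% to 1.79% |
| Rescue drug included, or table not windowed | AEs and SAEs | 9 × (24 − 13) = 99 to 30 × (24 − 13) = 330 | 1.38% to 4.58% |

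Some post-rescue time enters the AE and SAE tables on either reading, and no specified table removes it.

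**The case against.** **The SAP is silent rather than contrary.** Its overview list is introduced as inclusive, not exhaustive, and section 6 declares no safety departure, so the protocol text could be read as still in force. The amendment entry of 4 July 2017 says openly that the overview categories were updated to match earlier studies of the two drugs. This stands in part: a reader might infer a deliberate decision to drop the outputs, and the documents do not show one. But the SAP names two narrower discontinuation categories in place of the promised one. The amendment entry does not say that a protocol output was lost, and it does not touch the rescue analysis.

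**Little information is lost.** The AEs are still counted among all AEs and listed by patient, AESI categories have their own summaries, and the SAP plans no formal comparison of AEs between arms. This also stands in part. What is missing is a descriptive side-by-side count, not a test.

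**A stronger reading of AE reporting does not hold.** Protocol section 6.3.6 brings deteriorations in mandated laboratory values and vital signs into AE reporting if they meet an SAE criterion "or are the reason for discontinuation of treatment with the IP". Section 3.9.2 stops drug for a low eGFR "confirmed by a repeated central lab measurement within 1 week". A reader might infer that a non-serious laboratory deterioration is recorded as an AE only when it stopped drug, so that the missing table hides a whole class of events. Protocol section 5.2 also has investigators assess out-of-range results for clinical significance and report them as AEs accordingly, so the documents do not support that inference. The eGFR case remains one example of an event that the missing table would count. Renal impairment is also an AESI, and eGFR is summarised by arm.

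**A stronger reading of the laboratory window does not hold either.** SAP section 3.5.3 ends the window a fixed number of days after last dose without naming the drug, and blinded drug stops at rescue. A reader might infer that practically all laboratory values after rescue are discarded. The same section says values are kept whether or not the patient was rescued. SAP 4.2.3.1 and 4.2.5.3 treat the period before rescue as something separate from the main tables. Protocol Table 2 also sets rescue criteria for the intervals between visits, so one cannot say that no scheduled sample falls within the window. What is left is a point of wording.

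**Conclusion.** The two omissions are established by the text. Protocol section 8.5.6 promises a by-arm summary of AEs leading to discontinuation and an AE analysis excluding data after rescue. The SAP specifies neither and declares neither as a change.

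Their size is unknown, because the documents give no rates of AE-related discontinuation or of rescue. On the assumed rates above, about 2 to 14 patients per 300-patient arm would not be counted as stopping drug for an AE. Post-rescue time that no table separates would be about 0.1% to 4.6% of patient-time. The low end applies if last dose means blinded drug. The high end applies if rescue drug counts or the table has no window. These figures assume full follow-up and rescue at about Week 13.

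The primary and secondary efficacy results are unaffected. The point should be corrected because tolerability against each single agent is the stated safety objective and both outputs are the sponsor's own commitments. The undefined last dose is a minor clarification.

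**What to change.** - **Discontinuation.** Add a line to the overview in SAP section 4.2.5.1 for any AE leading to discontinuation of study medication, with a table by SOC and PT for each arm and SAEs shown as a subset. Keep the separate hypoglycaemia line, since those events are recorded on their own CRF pages.
- **Rescue.** Add AE and SAE summaries that exclude data after the first rescue dose, beside the main tables that include it.
- **Declaration.** If either output was left out on purpose, say so in SAP section 6 with the reason.
- **Clarification.** State in SAP section 3.5.3 and in the AE and AESI parts of section 4.2.5.1 that the on-treatment window for the main tables does not end at rescue. This agrees with protocol section 8.5.6 and with the SAP's own rule for laboratory values.

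The cost is SAP wording and a few more runs of existing tables. Protocol section 6.3.3 already collects "Action taken with regard to IP" for each AE, and rescued patients stay on the visit schedule, so no new data are needed.
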